### 1.2.3 Targeting of HPV-associated cancers with adoptive T cell therapy

In a clinical trial of HPV-16 E6 TCR T cells for patients with metastatic cancers associated with HPV-16 (e.g. cervical cancer, anal cancer, head and neck cancer, etc.), subjects received a chemotherapy conditioning regimen followed by E6 TCR T cells and aldesleukin (protocol 15-C-0005). Two of 12 patients experienced objective tumor responses. No E6 TCR T cell dose-limiting toxicities, off-target toxicity, healthy tissue targeting, or cytokine storm were observed. The maximum administered dose was deemed the maximum tolerated dose. Separately, in a clinical trial of autologous tumor-infiltrating T cells generated from cultures with HPV reactivity for metastatic HPV+ cancers, objective tumor responses occurred in 3/9 patients with cervical

cancer [11]. Adoptive T cell therapy has not been reported for the treatment of premalignant HPV-related diseases.

[figure not shown]
#### 1.2.4 E6 TCR discovery and characterization

HPV-16 E6 is a viral oncoprotein that is constitutively expressed by and important to the survival of HPV-16+ infected cells, and it is absent from healthy human tissues. We isolated a TCR from the tumor-infiltrating T cells of a patient with metastatic anal cancer that recognized the E629-38 epitope (described below).

[figure not shown]

**Figure 1. PG13-oDCA2-E6-C12 TCR vector map.** An MSGV1 retroviral vector encoding the TCR was constructed. This retroviral vector consists of 7,325 base pairs and includes a 5' LTR from the murine stem cell virus (promoter), packaging signal including the splicing donor (SD) and splicing acceptor sites (SA). Alpha and beta chains of the E6 TCR are linked by a P2A peptide.

Peripheral blood T cells transduced to express the E6 TCR displayed high avidity for the E629-38 peptide (Figure 2) and CD8-independent HLA-A\*02:01/E629-38 tetramer binding (Figure 3). They specifically recognized a panel of HPV-16+ HLA-A\*02:01+ cervical and oropharyngeal cancer cell lines. Thus, TCR gene engineered T cells expressing the E6 receptor can be used to target HPV-16+ HLA-A\*02:01+ cells.

[figure not shown]

**Figure 2.** T cells transduced to express the E6 TCR demonstrated high avidity for the E629-38 peptide. CD4 and CD8 T cells from PBMC were transduced to express the E6 TCR. Functional avidity was tested by coculture with T2 cells pulsed with titrated concentrations of E629-38 peptide.

**Figure 3. Peripheral blood T cells transduced to express the E6 TCR display CD8-independent HLA-A\*02:01/E629-38 tetramer binding.** T cells from PBMC were transduced to express the E6 TCR. Dot plots shown are gated on PI- lymphocytes.

In contrast to TCRs that have had unexpected cross-reactivity against normal human proteins, this TCR was isolated directly from a human T cell. Hence, it was subjected to thymic selection and is unlikely to possess avid reactivity against self-antigens. The complementarity determining regions of the TCR have not been modified, so there is no chance that cross-reactivity has been artificially introduced. The target epitope is derived from a viral protein, and no more than 6 of its 10 amino acids are shared with any human protein. There is no cross reactivity of this TCR against epitopes of these human proteins (Figure 4).

Gene Abbreviation	Sequence	Full Name of Protein
HPV16 E6 29-38	TIHDIILECV	HPV-16 E6 29-38
ITGA8	TISDTILEVG	Integrin alpha-8
DMBX1	TFQDIILEAR	Diencephalon/mesencephalon homeobox 1
ACO2	IIHQIILENY	Aconitate hydratase, mitochondrial
PTPRG	FIHDFILEAI	Protein tyrosine phosphatase
HPTPG	IIHDFILEAT	Receptor-type tyrosine-protein phosphatase gamma
PTPRU	FIHDAILEAC	Receptor-type tyrosine-protein phosphatase kappa or mu or U

**Figure 4. E6 TCR transduced T cells did not recognize T2 cells pulsed with peptides sharing  $\geq 6$  amino acids with peptides from human proteins identified by BLAST search. T2 cells pulsed with the peptides indicated in the table were cocultured with T cells expressing the E6 TCR.**

#### 1.2.5 High-dose Interleukin-2 (Aldesleukin)

Interleukin-2 (IL-2) is a T cell growth factor that has been administered as a single agent and in combination with adoptive T cell therapy for the treatment of cancer [12]. As a single agent it can induce regression of metastatic melanoma and renal cell carcinoma with overall response rates around 20% [13]. Although high quality published data comparing adoptive T cell therapy with and without IL-2 are lacking, data from animal models indicate that IL-2 enhances the anti-tumor function of adoptively transferred T cells [14, 15].

Single-agent high-dose aldesleukin for invasive cancers is administered at a fixed dose (600,000 or 720,000 IU/Kg) but a variable number of doses are given depending on individual tolerance of the drug. Aldesleukin infusions are continued until adverse events prohibit further drug administration. To increase that safety of the present protocol, aldesleukin dose number will be capped at two doses, a number of doses that has been well tolerated in prior studies [16, 17]. In prior studies, the toxicity of aldesleukin was not increased by coadministration of autologous T cells [18, 19].

#### 1.2.6 Safety Considerations

HPV-16 E6 TCR T cells target a foreign viral protein that is not present in human tissue. The TCR was discovered from the study of tumor infiltrating T cells isolated from a human and therefore has undergone thymic selection to not have human autoreactivity. The nucleotide sequence of the E6 TCR was codon optimized for expression in human tissues and the TCR constant regions replaced with their murine counterparts to improve TCR alpha/beta chain pairing and TCR expression. The alpha/beta TCR sequence was cloned into the MSGV1 retroviral vector, which has been tested extensively in clinical trials. TCR avidity enhancement was not performed and wild-type CDR regions are present, therefore there is no chance that off-target reactivity has been artificially introduced. The clinical safety of E6 TCR T cells has been studied in a protocol for the treatment of metastatic HPV-16 cancers (15-C-0005). In that study,

a conditioning chemotherapy regimen that enhances T cell survival and function, and increases the toxicity of the treatment was employed, and high-dose aldesleukin was administered to individual patient tolerance. Twelve patients were treated and no dose-limiting toxicity for E6 TCR T cell infusion was encountered. The E6 TCR T cells did not demonstrate off-target toxicity, targeting of healthy tissues, or cytokine storm. The maximum administered dose was thus declared to be the maximum tolerated dose ( $1.7 \times 10^{11}$  cells).

In the present protocol, the safety margin of the treatment has been increased by the following measures: 1) No conditioning chemotherapy will be given. 2) Aldesleukin dose number will be capped at two. 3) E6 TCR T cell dose will begin at dose level -1.

Experience at the NIH Clinical Center treating more than 200 patients with advanced cancers with genetically engineered T cells indicates that these cells do not have a significant risk of malignant transformation in this setting. While insertional mutagenesis is a known hypothetical risk, there has never been a reported vector-mediated gene transfer into mature T cells since the first NCI sponsored gene transfer study in 1989 [20]. This proposed protocol follows all current FDA guidelines regarding testing and follow up of patients receiving gene transduced cells.

## **2 ELIGIBILITY ASSESSMENT AND ENROLLMENT**

### **2.1 ELIGIBILITY CRITERIA**

#### **2.1.1 Inclusion Criteria**

- 2.1.1.1 Patients must have vulvar HSIL as confirmed by pathology report from a CLIA-certified laboratory.
- 2.1.1.2 Vulvar HSIL must be HPV-16+ by a PCR, RNA, or in situ hybridization test from a CLIA certified laboratory.
- 2.1.1.3 Patients must have measurable lesion(s) as defined in section 6.3.2 and one or more of the following criteria:
  - a. Failure of surgery to control disease (i.e. positive margins or recurrence of HSIL after surgery).
  - b. Multifocal or extensive disease for which surgery would result in major deformity that is not be acceptable to the patient.
  - c. Disease for which surgery would have a risk of functional impairment that is not be acceptable to the patient (i.e. involve partial or complete excision of the clitoris, anus, vagina, or urethra).
- 2.1.1.4 Patients may have received any previous therapy, including surgical excision, but must have histologically documented recurrence on new biopsy and a measurable lesion that meets the above criteria.
- 2.1.1.5 The presence of disease that can be biopsied for research purposes is not an inclusion criterion.
- 2.1.1.6 Patients must have the HLA-A\*02:01 allele

- 2.1.1.7 Age  $\geq 18$  years and  $\leq 65$  years. As age increases, the ability to tolerate the toxicities of aldesleukin decreases, so the patient population for this study will include up to and including 65 years of age to increase safety.
- 2.1.1.8 ECOG performance status of 0-1 as defined by **Appendix A**. Able to understand and sign the Informed Consent Document.
- 2.1.1.9 Women of child-bearing potential must have a negative pregnancy test. Women of child-bearing potential are defined as all women who are not post-menopausal or who have not had a hysterectomy. Postmenopausal will be defined as women over the age of 55 who have not had a menstrual period in at least 1 year.
- 2.1.1.10 The effects of E6TCR T Cells on the developing human fetus are unknown. For this reason, women of child-bearing potential must agree to use adequate contraception (hormonal or barrier method of birth control; abstinence) prior to study entry and for the duration of study participation. Should a woman become pregnant or suspect she is pregnant while she is participating in this study, she should inform her treating physician immediately.
- 2.1.1.11 Seronegative for HIV antibody. The experimental treatment being evaluated in this protocol depends on an intact immune system. Patients who are HIV seropositive can have decreased immune-competence and thus be less responsive to the experimental treatment.
- 2.1.1.12 Seronegative for hepatitis B antigen and hepatitis C antibody. If hepatitis C antibody test is positive, then the patient must be tested for the presence of antigen by RT-PCR and be HCV RNA negative.
- 2.1.1.13 Must be willing to participate in Gene Therapy Long Term Followup Protocol (15-C-0141), which will follow patients for up to 15 years per Food and Drug Administration (FDA) requirements.
- 2.1.1.14 Patients must have normal organ and marrow function as defined below:
- leukocytes  $\geq 3,000/\text{mcL}$
  - absolute neutrophil count  $\geq 1,000/\text{mcL}$
  - platelets  $\geq 150,000/\text{mcL}$
  - hemoglobin  $\geq 10.0 \text{ g/dL}$
  - total bilirubin within normal institutional limits except in patients with Gilbert's Syndrome who must have a total bilirubin  $< 3.0 \text{ mg/dL}$
  - AST(SGOT)/ALT(SGPT) Serum ALT/AST  $< 3\text{X ULN}$
  - creatinine  $< 1.5\text{X baseline}, < 1.5\text{X ULN}$
- OR
- creatinine clearance  $\geq 60 \text{ mL/min/1.73 m}^2$  for patients with creatinine levels above institutional normal (by the Chronic Kidney Disease Epidemiology Collaboration (CKD-EPI) equation)

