### 3.1.5 Dose Limiting Toxicities (DLTs)

All treatment related Grade 3 and greater AEs occurring within 30 days of the cell infusion will be considered DLTs with the exception of the following expected transient effects of aldesleukin.

- Grade 3 fever or chills responsive to symptomatic treatment that resolve to  $\leq$  grade 2 in 48 hours.
- Grade 3 hypotension or oliguria responsive to  $\leq$  1.5L of IV fluid boluses in 24 hours that resolves to  $\leq$  grade 2 in 48 hours.
- Grade 3 dyspnea/hypoxia that improves to  $\leq$  grade 2 or less with supplemental oxygen and resolves to  $\leq$  grade 2 without supplemental oxygen in 48 hours.
- Grade 3 creatinine or electrolyte abnormalities that resolve to  $\leq$  grade 2 in 48 hours.
- Grade 3 or higher white blood cell count decreased and/or lymphocyte count decreased that resolves to  $\leq$  grade 2 in 72 hours.

Further outline of expected AEs with aldesleukin and their management is included in [Appendix B](#) and [Appendix C](#).

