## 3.4 ON-STUDY EVALUATIONS

### 3.4.1 Prior to starting cell infusion:

Within 14 days prior to therapy, patients will have a complete blood count, serum chemistries performed including electrolytes, BUN, creatinine, pregnancy test and liver function

tests. If any results are beyond the criteria established for eligibility, the patient will not proceed until the abnormalities can be resolved.

- Pre-treatment biopsy within 8 weeks prior to therapy
- Blood samples for analysis for detection of Replication Competent Retrovirus (RCR) by PCR as described in Section 5.3.

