## 10 HUMAN SUBJECTS PROTECTIONS

### 10.1 RATIONALE FOR SUBJECT SELECTION

The patients to be entered in this protocol have vulvar HSIL that is unable to be completely resected to negative margins without causing deformity. As only women develop vulvar HSIL, men will be excluded from the study.

Subjects from all racial/ethnic groups are eligible for this study if they meet the eligibility criteria. To date, there is no information that suggests that differences in drug metabolism or disease response would be expected in one group compared to another. If differences in outcome that correlate to ethnic identity are noted, accrual may be expanded or a follow-up study may be written to investigate those differences more fully.

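### The renal entry criterion (2.1.1.14) aims a clearance floor of 60 at everyone above normal creatinine, but its OR means the floor cannot exclude anyone who meets the creatinine limits

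*Combined protocol and SAP*

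**What the plan says.** Section 2.1.1.14 opens with "Patients must have normal organ and marrow function as defined below". Its renal part has two limbs joined by OR:

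- Creatinine limb: below 1.5 times baseline, and below 1.5 times ULN. The two limits are separated only by a comma, and baseline is not defined.
- Clearance limb: at least 60 mL/min/1.73 m2, "for patients with creatinine levels above institutional normal (by the Chronic Kidney Disease Epidemiology Collaboration (CKD-EPI) equation".

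The exclusion criteria (2.1.2) contain no renal limit. Section 3.4.1 repeats the chemistry before infusion and refers back to the same criteria: "If any results are beyond the criteria established for eligibility, the patient will not proceed until the abnormalities can be resolved".

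The population is women only (10.1: "As only women develop vulvar HSIL, men will be excluded from the study") aged 18 to 65. Section 2.1.1.7 explains the age cap by declining tolerance of aldesleukin toxicity: "the patient population for this study will include up to and including 65 years of age to increase safety".

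**The concern.** The clearance limb names its own population: everyone whose creatinine is above institutional normal. The creatinine limb already accepts most of those women, namely those from 1.0 to just under 1.5 times ULN whose creatinine is also within 1.5 times baseline. Because the limbs are alternatives, a low clearance cannot keep such a woman out. The figure of 60 looks like a safeguard for raised creatinine, but on the literal text it is not one for this group.

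Two things are at stake. The first is safety: these women go on to aldesleukin, for which Appendix B lists creatinine increase in 33% and oliguria in 63% of treated patients. The second is who enters the dose-limiting toxicity (DLT) assessment. Section 3.1.5 exempts "Grade 3 creatinine or electrolyte abnormalities that resolve to" grade 2 or lower within 48 hours, and exempts grade 3 oliguria within stated fluid and time limits. Under 3.1.5 and Appendix C, events beyond those limits count as DLTs. At most 12 patients determine the maximum tolerated dose (MTD) (Section 8).

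**Working it through.** **Step 1: the logic.** Read the comma as AND. Write C for creatinine.

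- Limb 1: C < 1.5 × baseline AND C < 1.5 × ULN.
- Limb 2: C > ULN AND estimated clearance ≥ 60.
- Eligible = limb 1 OR limb 2.

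If limb 1 is true, the patient is eligible at any clearance. If the comma were read as OR, limb 1 would be wider and the floor would bind even fewer women. This step needs no outside figure.

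**Step 2: is it repaired elsewhere?** No. Section 2.1.2 adds no renal limit, and Section 3.4.1 only points back to 2.1.1.14.

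**Step 3: size.** Assumptions not in the documents: the CKD-EPI coefficients (the protocol names the equation but not the version) and a female ULN of 0.8 to 1.2 mg/dL. For women with C > 0.7 mg/dL:

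- 2009: 144 × (C/0.7)^−1.209 × 0.993^age (× 1.159 with the race coefficient)
- 2021: 142 × (C/0.7)^−1.2 × 0.9938^age × 1.012

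Example (2009 form): ULN 1.0, C = 1.49, age 65: 144 × 0.4012 × 0.6334 = 36.6.

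Estimated clearance at 1.49 × ULN, which limb 1 accepts if creatinine is also within 1.5 times baseline (2009 / 2021 / 2009 with race coefficient):

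| ULN (mg/dL) | Age 18 | Age 45 | Age 65 |
|---|---|---|---|
| 0.8 | 66.7 / 67.8 / 77.3 | 55.2 / 57.3 / 63.9 | 47.9 / 50.6 / 55.5 |
| 0.9 | 57.8 / 58.9 / 67.0 | 47.8 / 49.8 / 55.4 | 41.6 / 44.0 / 48.2 |
| 1.0 | 50.9 / 51.9 / 59.0 | 42.1 / 43.9 / 48.8 | 36.6 / 38.7 / 42.4 |
| 1.1 | 45.4 / 46.3 / 52.6 | 37.5 / 39.1 / 43.5 | 32.6 / 34.6 / 37.8 |
| 1.2 | 40.8 / 41.7 / 47.3 | 33.8 / 35.3 / 39.2 | 29.4 / 31.1 / 34.0 |

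At age 65 every entry is below 60. At a milder 1.2 × ULN and age 55, the range without the race coefficient is 41 (ULN 1.2) to 70 (ULN 0.8), so the gap shrinks or closes for small elevations and low ULNs.

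**Step 4: when limb 2 does decide.**

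- A woman who fails the baseline limit. Take ULN 1.0, baseline 0.60, C = 1.05, age 30. Then C is 1.75 × baseline and 1.05 × ULN, so limb 1 fails. Her clearance is 71 (2009) or 73 (2021), so limb 2 alone admits her. Below 60 she would be refused.
- A woman at exactly 1.5 × ULN. At ULN 0.8 the clearance is 66–67 at age 18 and 61–63 at age 30, so limb 2 admits her. At ULN 0.9 it is at most 58 without the race coefficient, but 66 at age 18 with it.

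**Step 5: link to the DLT rule (3.1.6).** One DLT among the first three patients on dose level -1 leads to three more patients there. On either level it takes two patients with DLTs to stop that level or the study. A renal DLT in one woman therefore changes the outcome only together with a DLT in another.

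**The case against.** The strongest reply is that the qualifier on the clearance limb shows the intent: clearance governs everyone above normal, and a careful screener would apply it. That reading is available, so the criterion is ambiguous rather than void. But it conflicts with the OR, and two screeners could decide opposite ways on the same woman.

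Four stronger inferences are tempting, and the documents do not support them.

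- *The floor never acts.* Step 4 shows that it can both admit and refuse.
- *The baseline limit is empty because screening is the first value.* Baseline is undefined and could be a prior chart value. Leukapheresis is at least 21 days before infusion (3.1.2) and the pre-infusion chemistry is within 14 days of therapy (3.4.1), so an earlier value may exist. The limit could then catch a rise, which is a reason to define it rather than delete it.
- *One renal DLT can stop a dose level.* Section 3.1.6 requires two. Section 3.1.5 also exempts transient creatinine and oliguria events, and Section 3.1.4 withholds the second aldesleukin dose for oliguria requiring boluses or for any grade 3 or higher event after the first.
- *The 33% and 63% in Appendix B apply here.* They come from the product label. Section 1.2.5 describes single-agent high-dose treatment for invasive cancers as continued until adverse events prohibit it, whereas this trial caps it at two doses.

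It is also fair to say that nothing in the documents shows how many candidates will have raised creatinine, or that such women would have more DLTs. The number may be small.

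**Conclusion.** The point holds in a limited form. On the text as written, the clearance floor cannot exclude any woman who meets the creatinine limb, although its wording is addressed to all women above normal. That conclusion rests on the documents alone.

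The size rests on the assumed ULN and the CKD-EPI coefficients. At 1.49 times ULN, estimated clearance is about 29 to 51 at age 65 and 34 to 57 at age 45, with upper ends of 56 and 64 under the 2009 race coefficient. At age 18 and a low ULN the value can exceed 60, so the gap is widest at the older ages for which Section 2.1.1.7 shows most concern.

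The effect on the MTD is a plausible route, not a demonstrated bias. The planned numbers (12 to determine the MTD, 18 intended) are not affected. It should be corrected because it bears on safety and on who enters the DLT assessment, and because the correction is cheap.

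**What to change.** Reconcile the two limbs of 2.1.1.14. The sponsor should:

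1. State whether the clearance figure governs every patient above institutional normal or is only an alternative route to entry, and word the connector to match.
2. Define baseline (which value, taken when), and say whether both creatinine limits must be met.
3. Align the normal-organ-function heading and the pre-infusion check in 3.4.1 with that decision.

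Which renal limit applies is for the sponsor to decide, and none is proposed here. When settling the heading, note that neither reading checks clearance in women whose creatinine is within normal limits. At an assumed ULN of 1.2 mg/dL and age 65, creatinine exactly at ULN gives 47 to 50 (55 with the race coefficient).

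The cost is one line in the protocol and the eligibility checklist. Creatinine is already measured at screening (2.2.3), so no new test is needed. If the clearance figure is made to govern, a few patients with mildly raised creatinine may become ineligible.

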### 2.1.2 Exclusion Criteria

- 2.1.2.1 Patients who are receiving any other investigational agents
- 2.1.2.2 Because there is an unknown but potential risk for adverse events in nursing infants secondary to treatment of the mother with E6 TCR, breastfeeding should be discontinued if the mother is treated with E6 TCR. These potential risks may also apply to other agents used in this study.
- 2.1.2.3 Uncontrolled intercurrent illness including, but not limited to, any ongoing or active infection (e.g. requiring anti-infective therapy), coagulation disorders, cardiovascular disorders, respiratory disorders, cancer, or psychiatric illness/social situations (within the last six months) that would limit compliance with study requirements.
- 2.1.2.4 Any form of systemic immunodeficiency, including acquired deficiency such as HIV or primary immunodeficiency such as Severe Combined Immunodeficiency Disease. The experimental treatment being evaluated in this protocol depends on an intact immune system. Patients who have decreased immune competence may be less responsive to the treatment.
- 2.1.2.5 Concurrent systemic steroid therapy if greater than the equivalent of 5 mg prednisone PO daily. Patients previously on steroids must be off steroids for four weeks prior to treatment.
- 2.1.2.6 Any history of clinically significant cardiac arrhythmia, coronary revascularization, ischemic symptoms, or previously documented LVEF of less than or equal to 45%. A cardiac stress test is required for all patients greater than 50 years old. A cardiac stress test may also be performed for any clinical concern. Patients with cardiac ischemia are not eligible.
- 2.1.2.7 Patients with any active invasive cancer are not eligible.
- 2.1.2.8 Patients vulvar HSIL that is not HPV-16+ or is associated with multiple types of high-risk HPV are not eligible.

